Inclusion criteria: all patients undergoing open shoulder surgery or shoulder arthroscopy. Exclusion criteria: anyone with a history of allergic reaction to chlorhexidine or benzoyl peroxide. Anyone with a history of previous shoulder infection, current open skin lesions around the shoulder or the use of current anti-acne medications around the shoulder.

Healthy volunteer portion: Healthy volunteers will respond to the study from fliers on campus. A cotton swab test on both shoulders will be performed prior to any treatment. If a threshold of P. Acnes is met (>1000 CFUs) then volunteers will be randomized to the same two groups and retested after three days of unilateral treatment. Finally, volunteers will undergo repeat cotton swab testing one week after 3 day wash was finalized.

3 * Describe the relevant prior experience and gaps in current knowledge. Describe any relevant preliminary data:

We have no preliminary data at this institution. Current P. Acnes shoulder burden is estimated to be 36% based on recent literature with a periprosthetic infection rate is at least 1-2% with this number expected to increase as more shoulder surgery is expected with the aging population. Economic impact after a shoulder surgical infection is tremendous with additional estimated hospital costs of over \$17,000 per infection not including the impact from wages lost (12).

4 * Provide the scientific or scholarly background, rationale, and significance of the research and how it will add to existing knowledge:

P.acnes is a gram-positive anaerobic bacillus that resides nonpathogenically in the sebaceous glands associated with hair follicles. P.acnes frequently becomes a pathogenic causing infection after arthroscopic and open shoulder procedures. Untreated infections of this nature present with shoulder pain, glenohumeral arthrosis, and arthroplasty failure months or years after a procedure(1). P.acnes forms a biofilm on implant surfaces; cultures taken at the time of surgical revision of failed shoulder arthroplasties are commonly positive for the bacteria(2).

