Patients will receive standard of care for all diagnostic or treatment purposes. They will be indicated for shoulder surgery as is the usual protocol. All procedures in the operating room will be under usual protocol including skin prep, sterile procedure as well as a usual post operative protocol and follow up. Patients will be followed to document infection, as would be standard of care as well. Monitoring will be at 2 weeks, 6 weeks, 3 and 6 months as well as 12 months which are standard visits after shoulder surgery and based on the standard protocol of asking the patient about their symptoms. No additional testing will be performed. Patient demographics will be reviewed from the chart.
- * Describe the duration of an individual participant's participation in the study:**

Patients will be monitored for the standard signs of infection for one year after shoulder surgery.

Healthy Volunteers will participate for about 12 days.
- * Describe the amount of time it will take to complete the entire study:**

24 months total. 6 month enrollment period. 12 month follow up. 6 month data analysis and manuscript preparation.
- * Describe any additional participant requirements:**

N/A

ID: VIEW4E0280585B400
Name: v2_Study Procedures

Sample Size and Data Analysis

If you uploaded a separate research protocol document in the 'Research Protocol' page, cite the applicable section and page numbers from that document in the answer boxes below.

- 1 * Provide the rationale and sample size calculations for the proposed target population:
Power analysis. In primary shoulder surgeries, the overall incidence of P. Acnes is 36% in a recent series. We expect a 2/3 decrease in intraoperative incidence. Ninety eight patients are necessary, a 20% attrition rate is expected so a goal of 160 people to be recruited total and about 1/4 to be healthy volunteers.

See below from Stata/SE 13.0 for Mac (64-bit Intel), Revision 17 Jun 2013

```
power twoproportions 0.36 0.12, test(chi2)
Performing iteration ...
Estimated sample sizes for a two-sample proportions test
Pearson's chi-squared test
Ho: p2 = p1 versus Ha: p2 != p1
```

Study parameters:

```
alpha = 0.0500
power = 0.8000
delta = -0.2400 (difference)
p1 = 0.3600
p2 = 0.1200
```

```
Estimated sample sizes: N = 98
N per group = 49
```

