The risks of using OTC safe topical skin preps are low to the individual patient. Risks of a breach of confidentiality are also low. The overall benefit of reducing surgical site infection would be in the reduction of healthcare costs and a quicker recovery for patients. The potential benefits exceed the risks.

4 * Describe the alternatives to participation in this study. If there are no alternatives, state that participation is voluntary and the alternative is not to participate. For intervention studies, describe appropriate alternative clinical procedures or courses of

treatment available to subjects.

Participation is voluntary and the alternative is to not participate.

ID: VIEW4E1B5251B0400
Name: v2_Potential Benefits and Alternatives

Withdrawal of Participants

If the questions below are not applicable to the research (i.e., chart review), enter "N/A".

- * Describe anticipated circumstances under which subjects will be withdrawn from the research without their agreement:**
A participant may be withdrawn from the study without consent if the PI decides to end the study. Other reasons for removing a participant without consent may include but are not limited to non-adherence with the protocol and/or therapy, and inappropriate behavior towards study personnel.
- * Describe procedures for orderly termination:**
N/A
- * Describe procedures that will be followed when subjects withdraw from the research, including partial withdrawal from procedures with continued data collection:**
Should a participant terminate the study prematurely, if at all possible, all evaluation at 12 month visit will be finalized at his/her final visit.

ID: VIEW4E1B52531F800
Name: v2_Withdrawal of Participants

Privacy of Participants

If the study does not involve interaction with participants, answer "N/A" to the questions below.

- * Describe how you will ensure the privacy of potential participants throughout the study (*privacy refers to persons and their interest in controlling access to themselves*):**
It is the investigator's responsibility to conduct the protocol under the current version of Declaration of Helsinki, ICH Guidelines, Good Clinical Practice, and rules of local IRBs. The investigator must ensure that the patient's anonymity be maintained in their data submission to the Data Coordinating Center.

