Patients will be identified only by an identification code but not by their name, SSN, or hospital medical record number. Study Site Investigators will maintain a separate confidential enrollment log which matches identifying codes with the patients' names and addresses available only to local clinic staff.

All study forms, reports, and other records that are part of the study data collection materials will be identified by coded number to maintain patient confidentiality. All paper records will be kept in locked file cabinets. All electronic records of study data will be identified by coded number. Clinical information will not be released without written permission of the patient, except as necessary for monitoring by the IRB. Consent procedures and forms, and the communication, transmission and storage of patient data will comply with individual site IRB for compliance with The Health Insurance Portability and Accountability Act (HIPAA).

Regarding privacy, patients will not be contacted for further information or asked to revisit the medical center for any repeat visits. No further information will be further relayed other than the time of consent. Confidentiality and protection of patient information as stated above is an extension of the patient's privacy.
- * Describe the location where potential participants will receive research information and detail the specific actions the study team will take to ensure adequate privacy areas:**
Potential participants will receive information in private clinic rooms or private clinical/hospital areas with a curtain drawn for additional privacy.
- * Describe potential environmental stressors that may be associated with the research:**
There are no environmental stressors associated with the research.
- * Will this study have a site based in the European Union?**
 Yes No
- * Will the study have planned recruitment or data collection from participants while they are located in the European Union?**
 Yes No

Access link below for information about the EU General Data Protection Regulations to assist in answering these questions.
<https://www.umaryland.edu/oac/general-data-protection-regulation/>

ID: VIEW4E1B525B87C00
Name: v2_Privacy of Participants

Confidentiality of Data

- * Will stored research data contain identifiers or be able to be linked to and identify individual participants (either directly or through a code/research ID)?**
Yes

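### An early leaver's last visit can stand in for the 12-month infection evaluation, and the no-contact sentence contradicts the planned follow-up, so some late infections may be missed

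*Combined protocol and SAP*

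**What the plan says.** Four places in the combined protocol and SAP bear on this.

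- **Study Procedures** sets the follow-up: "Patients will be monitored for the standard signs of infection for one year after shoulder surgery". The schedule reads "Monitoring will be at 2 weeks, 6 weeks, 3 and 6 months as well as 12 months which are standard visits after shoulder surgery". Infection is judged by asking patients about symptoms, with no added testing.
- **Withdrawal of Participants**, third question: for a participant who stops early, and where feasible, "all evaluation at 12 month visit will be finalized at his/her final visit". The form's question covers partial withdrawal with continued data collection; the answer describes none.
- **Privacy of Participants**, first question: "patients will not be contacted for further information or asked to revisit the medical center for any repeat visits".
- **Justification, Objective, & Research Design**, item 4: "Untreated infections of this nature present with shoulder pain, glenohumeral arthrosis, and arthroplasty failure months or years after a procedure".

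Item 2 of that last section plans a reminder telephone call two days before surgery, and the resources section says that follow-up visits take place in a private clinic room. Sample Size and Data Analysis, item 2, gives no analysis of infection, no missing-data rule and no censoring rule.

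**The concern.** An evaluation made at week 6 describes six weeks of follow-up. If it is filed as the 12-month evaluation, nothing on the form shows that the remaining time was not observed. The plan's own background says that these infections can appear late, so the unobserved part of the year matters.

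The privacy sentence makes this worse. Taken at its word, it leaves no stated way to reach a patient who misses a visit, and it is at odds with the contacts and visits that the plan itself schedules.

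At stake is the one-year infection rate. Lowering shoulder infection is part of the stated purpose of the research, and it is the only direct benefit named for patients. A reported rate should rest on time that was actually observed.

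**Working it through.** **The plan's own calculation, and why it is not touched.** Inputs from Sample Size and Data Analysis, item 1: proportions 0.36 and 0.12, two-sided alpha 0.05, power 0.80. With the pooled-variance formula and mean proportion 0.24:

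- n per group = [1.960 × √(2 × 0.24 × 0.76) + 0.842 × √(0.36 × 0.64 + 0.12 × 0.88)]² / 0.24²
- = (1.184 + 0.488)² / 0.0576 ≈ 48.5, rounded up to 49, so 98 in total.

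This matches the plan (power at 49 per group is 80.4%). It concerns P. acnes incidence. Patient cultures are taken on the day of surgery, before any postoperative loss, so the point here does not affect it.

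**The passages side by side.**

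| Topic | One place | Another place |
|---|---|---|
| Time covered by the infection result | One year (Study Procedures) | Up to the last visit attended (Withdrawal of Participants) |
| Contact with patients | Reminder call (Justification, item 2) | No contact for further information (Privacy of Participants) |
| Return visits | Five visits to 12 months (Study Procedures) | Not asked back for repeat visits (Privacy of Participants) |

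**Size of the effect on the infection rate.** Inputs:

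- Recruitment of 160 with about 1/4 healthy volunteers (Sample Size and Data Analysis): 160 × 3/4 = 120 surgical patients.
- Infection rate of at least 1-2%, stated for periprosthetic infection (Justification, item 3), applied here to all surgical patients as an assumption.
- Postoperative loss of 20%, spread evenly over 12 months. This is an assumption; the plan states 20% attrition for the culture-based sample size.
- Infections arise at a constant rate over the year, unrelated to leaving. This is also an assumption.

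Steps:

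1. Leavers: 120 × 0.20 = 24.
2. Unobserved time: 24 × 6 months on average = 144 of 120 × 12 = 1,440 patient-months, or 10%.
3. Expected infections: 120 × 1% = 1.2, to 120 × 2% = 2.4.
4. Expected to be missed: 0.10 × 1.2 = 0.12, to 0.10 × 2.4 = 0.24.
5. Recorded rate if the missed cases count as absent: (1.2 − 0.12)/120 = 0.9%, to (2.4 − 0.24)/120 = 1.8%.
6. Outer case, in which every infection among leavers comes after exit: 24 × 1% = 0.24, to 24 × 2% = 0.48 missed; recorded rate 0.8% to 1.6%.
7. Observed time only, under the assumptions of step 4: 1.08/1,296 × 12 = 1.0%, to 2.16/1,296 × 12 = 2.0%. The downward bias goes.

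**The case against.** The strongest reply is that the withdrawal sentence may describe no more than an ordinary early-termination assessment. It is hedged by feasibility, and the plan nowhere says how infection status is coded after exit: absent, missing or censored. This stands in part. A reader might infer that late infections will be recorded as absent, and the documents do not support that as fact. But the hedge governs whether the early evaluation takes place, not what it can show, and no rule prevents it from being read as the one-year result.

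Second, the no-contact sentence is a privacy statement, not a withdrawal rule. It may mean no contact beyond what is described elsewhere, and the 12-month schedule consists of standard-care visits. Medical records are a listed data source (Prospective Data), so chart review remains open. This stands as far as intent goes. The literal wording still covers all patients and contradicts other sections.

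Third, infection is not a named endpoint. Aims 1 and 2 concern P. acnes burden, and no infection comparison between arms is planned. A reader might infer that a safety endpoint or a treatment comparison is biased; the plan contains neither. With 60 patients per arm and a two-thirds reduction from 1-2%, power would be only about 7-9% even with complete follow-up. This objection stands and confines the point to the descriptive rate.

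**Conclusion.** The point holds as a matter of reconciliation and follow-up accounting. Followed as written, the plan lets an early status serve as the 12-month infection evaluation, gives no rule for status after exit, and contradicts its own contacts and visits. Some late infections among early leavers may be missed or counted as absent, with a slight downward bias in the one-year rate.

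The bias is about 0.12 to 0.24 infections, or 0.9-1.8% recorded in place of 1-2%. It rests on the assumed 20% even postoperative loss, a constant infection rate, and the periprosthetic figure applied to every surgical patient, although arthroscopy is also eligible.

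A reader might note that one missed case would be 1/2.4 = 42% to 1/1.2 = 83% of the expected total and take that as the size of the problem. It is not: it supposes that a whole case is lost, while the same inputs predict a loss of 10% of the expected total. The primary P. acnes comparison stands as planned.

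**What to change.** 1. Reconcile Study Procedures, Withdrawal of Participants and Privacy of Participants on follow-up and contact.
2. In Withdrawal of Participants, state that infection status at early exit is recorded with its actual date and is not entered as the 12-month result. With the participant's agreement, take status through 12 months from the chart, which is already a data source.
3. In Sample Size and Data Analysis, state that only observed time counts toward the one-year infection rate, with early leavers censored at their last known status (a Kaplan-Meier estimate would do this and does not need a constant rate).
4. In Privacy of Participants, reword the no-contact sentence so that it allows the planned reminder call, the scheduled visits and a call about a missed visit, subject to agreement with the consent form.

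The cost is a few wording changes, one date field on the follow-up form and a small number of calls; telephone numbers are already listed under Protected Health Information. Some participants will be reported with incomplete follow-up, and a small IRB or consent wording amendment may be needed. The consent pages are not available here, so what they promise about contact must be checked first.
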